6.9.2. Objective Response Rate (ORR)

6.9.2.1. Primary Analysis

ORR is a summary measure of best overall response (BOR) as defined by RECIST Version 1.1. BOR is defined as the best response designation for each patient that is recorded between the date of the first dose of seliperatinib and the date of documented disease progression per RECIST 1.1 or the date of subsequent therapy, whichever occurs first. Each patient's BOR will be categorized as complete response (CR), partial response (PR), stable disease (SD), progressive disease (PD) or not evaluable (NE).

Response (PR or CR) must be confirmed by a repeat assessment performed no less than 28 days after the criteria for response are first met. In the event that the confirmation of a CR or PR occurs at a time point following an NE assessment, the best overall response will be CR or PR. That is, the sequence of time point responses CR-NE-CR (or PR-NE-PR/CR) will be considered a best overall response of CR (or PR). When stable disease is believed to be the best response, it must also meet the minimum interval of 6 weeks (42 days) from the start of study treatment. If

the minimum time is not met when stable disease is otherwise the best time point response, the patient's best response depends on the subsequent assessments. For example, a patient who has stable disease at the first assessment, progressive disease at the second and does not meet minimum duration for stable disease, will have a best response of progressive disease. The same patient lost to follow-up after the first stable disease assessment will be considered inevaluable.

The ORR is defined as the number of patients who achieve a BOR of CR or PR that are confirmed divided by the total number of patients in the analysis population. The point estimate will be accompanied by a 2-sided 95% exact binomial CI using the Clopper-Pearson method.

The primary analysis of ORR is based on the response assessment by the IRC. The efficacy of selpercatinib will be demonstrated primarily on the primary efficacy analysis population. ORR will also be summarized by cohort (1 & 2), as well as by major tumor types across cohorts.

6.9.2.2. Supportive Analysis

The analysis will be repeated based on investigator assessment of response.

The tumor-burden change will be calculated for each patient in the PAS as the percentage change from baseline in the sum of diameters of target tumor lesions at each assessment time point. The best tumor-burden change will be summarized descriptively by calculating the median and interquartile range across patients. Waterfall plots will be used to depict graphically the best change for each patient. Swimmer plots will be used to show the occurrence of clinical outcomes of interest over time (e.g. TTR, DOR, PD, treatment discontinuation, death).

Additional supportive analyses may be performed.

6.9.3. Time to Response (TTR)

TTR is defined as the number of months elapsed between the date of the first dose of selpercatinib and the first documentation of objective response (CR or PR, whichever occurs earlier) that is subsequently confirmed. IRC assessments will serve as the principal data source. Additional analyses based on investigator assessment will be provided.

TTR will be calculated as follows for patients who have a best overall response of confirmed CR or confirmed PR:

$$\text{TTR (months)} = (\text{Response Start Date} - \text{First Dose Date} + 1) / 30.4375$$

TTR will be summarized descriptively by calculating the median, IQR, minimum and maximum values. The number and percentage of patients with TTR by the following time points, measured relative to the date of first dose will be tabulated:

- <2 months
- 2 to 4 months
- 4 to 6 months
- 6 to 9 months
- \geq 9 months

Kaplan-Meier curves will be used to present graphically the TTR distribution over time.

6.9.4. Time to Best Response (TTBR)

TTBR is defined as the number of months elapsed between the date of the first dose of selpercatinib and the first documentation of CR (if patient's BOR is confirmed CR) or PR (if patient's BOR is confirmed PR) that is subsequently confirmed. IRC assessments will serve as the principal data source. Additional analyses based on investigator assessment will be provided.

TTBR will be calculated as follows for patients who have a best overall response of confirmed CR or confirmed PR:

$$\text{TTBR (months)} = (\text{Best Response Start Date} - \text{First Dose Date} + 1) / 30.4375$$

TTBR will be summarized descriptively in the same manner as TTR.

6.9.5. Duration of Response (DOR)

DOR is defined as the number of months from the start date of PR or CR (whichever response is recorded first), and subsequently confirmed, to the date of disease progression or death, whichever occurs earlier. Patients with time point responses such as PR-NE-PR or PR-Stable-PR will be considered confirmed. For such patterns of response, the start date will be based on the date of the initial response. IRC assessments will serve as the principal data source. Additional analyses based on investigator assessment will be provided.

DOR will be calculated as follows for patients who have a best overall response of confirmed CR or confirmed PR:

$$\text{DOR (months)} = (\text{Event/Censoring Date} - \text{Response Start Date} + 1) / 30.4375$$

DOR will be right-censored for patients who meet one or more of the following conditions:

- Subsequent anticancer therapy in the absence of documented disease progression
- Died or documented disease progression after missing two or more consecutively scheduled disease assessment visits
- Alive and without documented disease progression on or before the data cutoff date

If a patient meets more than one of these conditions, then the scenario that occurs first will be used for the analysis. The event or censoring date will be determined based on the conventions listed in [Table 6.1](#).

Table 6.1. Date of Event or Censoring for DOR

Situation	Date of event or censoring	Outcome
Death or disease progression between planned disease assessments	Date of death or first disease assessment showing disease progression, whichever occurs first	Event

Subsequent anticancer treatment started before disease progression or death (without disease progression beforehand)	Date of last evaluable disease assessment prior to start of subsequent anticancer treatment	Censored
Death or disease progression after missing two or more consecutively scheduled disease assessments	Date of last evaluable disease assessment visit without documentation of disease progression before the first missed visit	Censored
Alive and without disease progression	Date of last evaluable disease assessment	Censored

The patient's overall response status as of the data cutoff date will be summarized by tabulating the number and percentage of patients with confirmed CR or PR as follows:

- Response continuing
- Subsequent anticancer therapy without documented disease progression beforehand
- Documented disease progression
- Died (for patients who did not have documented disease progression beforehand)

DOR will be summarized descriptively using the Kaplan-Meier method with the 95% CI about the median calculated using Greenwood's formula.

6.9.6. Clinical Benefit Rate (CBR)

CBR will be calculated based on the proportion of patients with best overall response confirmed CR, PR, or stable disease lasting 16 or more weeks. Stable disease will be measured from the date of the first dose until the criteria for disease progression are first met. The analysis of CBR will be based on the methods described for ORR and will be presented in the summary table of best overall response and ORR.

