2.2 Secondary Objectives

- To assess the anti-tumor activity of selpercatinib by determining
 - ORR based on RECIST v1.1 as assessed by Investigator;
 - Duration of response (DOR) as assessed by IRC and Investigator;
 - Central nervous system (CNS) ORR based on RECIST v1.1 as appropriate to tumor type, as assessed by IRC (for patients with brain metastases);
 - CNS DOR as assessed by IRC (for patients with brain metastases);
 - Time to response (TTR) based on RECIST v1.1 as appropriate to tumor type, as assessed by IRC and Investigator;
 - Time to best response (TTBR) based on RECIST v1.1 as appropriate to tumor type, as assessed by IRC and Investigator;
 - Clinical Benefit Rate (CBR) based on the proportion of patients with best overall response of complete response (CR), partial response (PR), or stable disease (SD) lasting 16 or more weeks following initiation of selpercatinib, as assessed by IRC and Investigator;
 - Progression-free survival (PFS) as assessed by IRC and Investigator;
 - Overall survival (OS) following initiation of selpercatinib.
- To determine the safety profile and tolerability of selpercatinib.
- To characterize the PK properties of selpercatinib.

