| | Up to 28 days prior to first dose | D1 ±2 Days | D8 ±2 Days | D15 ±2 Days | D22 ^d ±2 Days | ±2 Days | EOT ^a ≤ 7 days | D 28 ±7 days | |
| Informed Consent ^e | X | | | | | | | | |
| Inclusion/exclusion criteria | X | | | | | | | | |
| Medical, surgical, malignancy history | X | | | | | | | | |
| Molecular Pathology Report(s) describing RET and other alterations ^f | X | | | | | | | | |
| Archived tumor tissue or fresh biopsy ^g | X | | | | | | | | |
| Physical examination and ECOG ^h | X | X | X | X | | D1 C2, 3, 4, 5, etc. | X | X | |
| Vital signs ⁱ | X | X ^j | X ^j | X ^j | | D1 C2, 3, 4, 5, etc. | X | X | |
| 12-lead ECG ^k | X | X | X | | | D1 C2-6 and every 12 weeks | X | X ^l | |
| Urine or serum pregnancy test ^m | X | X | | | | D1 C2, 3, 4, 5, etc. | | | |
| Hematology ⁿ | X | X | X | X | | D1 C2, 3, 4, 5, etc. | X | X | |
| Serum chemistries ^o | X | X | X | X | | D1 C2, 3, 4, 5, etc. | X | X | |
| Liver function tests ^p | | | | | | C2D15 and C3D15 | | | |

| Visit Window | Screening | Cycle 1 | | | | Cycle 2-higher | SFU ^b | | LTFU ^c |
|--|-----------------------------------|---------------|---------------|----------------|-----------------------------|--|------------------------------|-----------------|-------------------|
| | Up to 28 days prior to first dose | D1 ±2 Days | D8 ±2 Days | D15 ±2 Days | D22 ^d ±2 Days | ±2 Days | EOT ^a ≤ 7 days | D 28 ±7 days | |
| Coagulation ^q | X | X | | | | | | | |
| Thyroid panel ^t | X | | | X | | D1 of odd cycles beginning with C3 (C3, 5, 7, etc.) | | | |
| Urinalysis ^s | X | | | X | | D1 C2, and as clinically indicated. | X | X | |
| Calcitonin, CEA (MTC only) ^t | X | X | | X | | D1 C2 and odd-numbered cycles, starting with C3 through C13. Every 12 weeks thereafter (±7 days of each radiologic disease assessment) | X | | |
| Thyroglobulin (non-MTC thyroid cancers only) ^u | X | X | | X | | D1 C2 and odd-numbered cycles, starting with C3 through C13. Every 12 weeks thereafter (±7 days of each radiologic disease assessment) | X | | |
| Blood cortisol, ACTH, 24-hour urine for free cortisol ^v | X | X | | X | | D1 C2 and odd-numbered cycles, starting with C3 through C13. Every 12 weeks thereafter (±7 days of each radiologic disease assessment) | X | | |
| Disease assessment ^w | X | | | | | Perform assessments at week 4 (±7 days, optional) and week 8 (±7 days) and then every 8 weeks (±7 days) until week 48 following C1D1 and then every 12 weeks (±7 days) | X ^x | | X ^y |

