- Thyroglobulin: for patients with non-MTC thyroid cancer only, unless not measurable due to presence of anti-thyroglobulin antibodies): Day 1 of C2 and odd-numbered cycles, starting with C3 through C13, and every 12 weeks thereafter (± 7 days of each radiologic disease assessment). For each patient, all tests for thyroglobulin should be performed in the same laboratory to minimize intra-patient, lab-to-lab variability in their measurement.
- Blood cortisol, ACTH, 24-hour urine for free cortisol: for patients with Cushing's disease related to their cancer. Day 1 of C2 and odd-numbered cycles, starting with C3 through C13, and every 12 weeks thereafter (± 7 days of each radiologic disease assessment). If done, urine collection should begin pre-dose.
- Radiographic disease assessment: every 8 weeks (± 7 days) beginning with C3D1 through C13D1, and every 12 weeks (± 7 days) thereafter until PD, withdrawal of consent, or initiation of a new anticancer therapy(ies), including imaging of the chest, abdomen, and pelvis, utilizing the same modality(ies) as used for the baseline imaging assessment. Additionally, any studies performed at baseline that are positive for sites of disease should be repeated at all post baseline assessments. Additional studies can also be performed as clinically indicated. Please refer to the Imaging Manual for guidelines on how the various imaging studies should be performed.

Notes:

- Patients who discontinue study drug for reasons other than PD (e.g., AE, noncompliance, etc.) may (but, for practical reasons and to minimize patient inconvenience, are not required to) have scans performed and collected as defined above.
- Post-baseline imaging of the brain using the same modality as at baseline should be performed for patients with evidence of CNS disease at baseline and if clinically indicated.
- If consistent with local regulatory guidelines, an initial post-baseline assessment after 4 weeks of treatment (± 7 days) is encouraged. If this scan is performed, the next scan should continue according to the schedule above (beginning at C3D1).
- If consistent with local regulatory guidelines, confirmatory imaging a minimum of 4 weeks (e.g., 28 days) after the first imaging studies that demonstrate a tumor CR or PR by RECIST 1.1 is encouraged. If this scan is performed, the next scan should continue according to the schedule above.

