6.1.2. Definitions and Conventions

The **baseline value** is the last value observed prior to the first dose of study drug

The **study day** will be calculated in reference to the first dose date of selpercatinib as follows:

- assessment date/event date – first dose date + 1, if assessment date or event date \geq first dose date,
- assessment date/event date – first dose date, if assessment date or event date < first dose date.

Unless otherwise noted, **summaries of continuous variables** will include a mean, median, standard deviation, minimum, and maximum.

Unless otherwise noted, **summaries of categorical variables** will include the frequency and percentage (relative to the population being analyzed) of each category.

Duration is calculated as:

- Duration (days): (End date – Start date + 1)
- Duration (weeks): (End date – Start date + 1) / 7
- Duration (months): (End date – Start date + 1) / 30.4375
- Duration (years): (End date – Start date + 1) / 365.25

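### Because the clinical benefit rate runs stable disease to the date PD is found, PD at an on-time week-16 scan counts as stable disease of at least 16 weeks

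*SAP*

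**What the plan says.** SAP 6.9.6 defines CBR as the proportion of patients with "best overall response confirmed CR, PR, or stable disease lasting 16 or more weeks". It then fixes the SD clock: "Stable disease will be measured from the date of the first dose until the criteria for disease progression are first met". Protocol 2.2 sets the same threshold, "stable disease (SD) lasting 16 or more weeks following initiation of selpercatinib", without saying where SD ends.

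Three other places determine how the rule behaves:

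- **Scan calendar.** The disease-assessment row of Protocol Table 7-1 asks for scans at "week 8 (±7 days) and then every 8 weeks (±7 days) until week 48 following C1D1". Protocol 7.3 gives the same calendar by cycle: "every 8 weeks (± 7 days) beginning with C3D1 through C13D1".
- **Duration formula.** SAP 6.1.2: "Duration (weeks): (End date – Start date + 1) / 7".
- **Minimum for a best response of SD.** SAP 6.9.2.1: "it must also meet the minimum interval of 6 weeks (42 days) from the start of study treatment".

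Neither document requires a scan without PD at or near week 16 before SD counts towards CBR.

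**The concern.** The 16-week threshold coincides with the second required scan. Under SAP 6.9.6, SD ends on the day PD is found, so the scan that shows the disease is no longer controlled is also the scan that completes the 16 weeks. Someone last seen with SD at about week 8 is then reported as having had SD for at least 16 weeks.

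The same rule classifies patients by appointment date. Two patients with the same sequence, SD and then PD, can fall on opposite sides of the threshold because one came a few days early, although both were scanned within the protocol's window.

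CBR is a named secondary endpoint by both IRC and investigator. A reader will take it as the share of patients whose disease was controlled for 16 weeks, and as written it can include patients already shown to have progressed at week 16.

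**Working it through.** **Inputs.** Cycles of 28 days (Protocol 3.3); scans every 8 weeks from C3D1, ±7 days (Protocol Table 7-1 and 7.3); duration in weeks = (end − start + 1)/7 (SAP 6.1.2); SD starts at first dose and ends when PD is first found (SAP 6.9.6); minimum for a best response of SD, 42 days (SAP 6.9.2.1).

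**Step 1: reproduce the calendar.** The study day of cycle k, day 1 is 28(k − 1) + 1.

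- C3D1: day 57, 56/7 = 8 weeks after first dose.
- C5D1: day 113, 112/7 = 16 weeks.
- C13D1: day 337, 336/7 = 48 weeks.

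This agrees with the protocol's week 8 and week 48, so the second required scan is C5D1, week 16.

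**Step 2: best response of SD.** The week-8 scan falls on days 50 to 64. Even day 50 exceeds the 42-day minimum, so SD at week 8 is enough for a best overall response of SD. By Protocol Table 11-9, an unconfirmed PR at week 8 followed by PD also becomes SD once the minimum is met.

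**Step 3: PD found at the week-16 scan.** On the nominal day 113, duration = 113/7 = 16.14 weeks, which meets the threshold. Without the +1, or ending SD the day before the PD scan, it is 112/7 = 16.00 weeks, which still meets it.

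**Step 4: across the ±7-day window (days 106 to 120).**

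| Study day PD is found | SAP duration (weeks) | Counted in CBR? |
|---|---|---|
| 106 | 106/7 = 15.14 | No |
| 111 | 111/7 = 15.86 | No |
| 112 | 112/7 = 16.00 | Yes |
| 113 (nominal) | 113/7 = 16.14 | Yes |
| 120 | 120/7 = 17.14 | Yes |

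PD counts as benefit on 9 of the 15 window days (112 to 120) and not on the other 6. Without the +1 it counts on 8 of 15.

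**Step 5: when control was last shown.** In all these cases the last required scan without PD is the week-8 scan: day 57 (57/7 = 8.1 weeks), range day 50 to 64 (7.1 to 9.1 weeks).

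**Step 6: effect on CBR.** Each such patient adds 1/20 = 5 percentage points in a cohort of 20. For illustration, assume 12 of 20 patients otherwise benefit. SAP 6.9.6 takes its methods from ORR, so the intervals are exact 95%.

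| SD-then-PD patients added | CBR | 95% CI |
|---|---|---|
| 0 | 12/20 = 60% | 36 to 81 |
| 1 | 13/20 = 65% | 41 to 85 |
| 2 | 14/20 = 70% | 46 to 88 |
| 3 | 15/20 = 75% | 51 to 91 |

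**The case against.** The strongest defence is that this is a stated convention and agrees with the rest of the SAP. The DOR and PFS tables also date progression at the first assessment showing PD, so the SD part of CBR is in effect PFS of at least 16 weeks. True progression lies somewhere between two scans: the PD-scan date overstates SD and the last scan without PD understates it. The protocol speaks of a duration and sets no week-16 landmark.

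That is sound for a time-to-event summary. It does not rescue a yes/no threshold placed on a scan date. When PD is seen at the nominal week-16 scan, progression arose in an interval that ends at the threshold, so the patient had already progressed by week 16. For patients scanned on time, the criterion asks for little more than no PD at week 8.

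Several stronger readings are tempting, and the documents do not support them:

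- **That about 60% of SD-then-PD patients will be counted.** The 9 of 15 days becomes a proportion of patients only if scans are spread evenly over the window. The documents give no scan-date distribution. If scans are on time, all such patients count.
- **That the inflation is large.** Protocol 1.5 reports ORRs of 64% to 85% in the earlier study. If similar rates held here (an assumption), non-responders would number about 3 to 7 of 20 (0.15 × 20 = 3; 0.36 × 20 = 7.2), and only some of them would have SD and then PD at the week-16 scan.
- **That the SAP has two conflicting SD-duration rules.** The 42-day rule decides whether SD can be the best response; SAP 6.9.6 decides how long it lasted. These are different questions.
- **That the rule breaks down because it gives no SD end date for patients who never meet PD.** This is missing detail that a sentence can supply. A scan at end of treatment is required if none was done in the last 8 weeks (Table 7-1; two cycles in Protocol 7.4).

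It also stands that CBR carries no hypothesis or decision rule, and that a patient-level PFS listing would let a reader find these patients.

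**Conclusion.** The concern holds for CBR alone. As written, SD at week 8 followed by PD at an on-time week-16 scan is reported as SD of at least 16 weeks, and this is so under every duration convention tried. The same course scanned 2 to 7 days early is not counted. Relative to a rule that requires disease control to be shown at week 16, CBR is biased upward, and it varies with scan timing that the protocol permits.

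The size is 5 points per affected patient in a cohort of 20. Because SAP 6.9.1 bases the primary efficacy analyses on tumour-type subgroups, the step is 100/n points for a subgroup of n patients. The number affected cannot be derived from the documents and is probably small. ORR, the primary endpoint, does not use this rule. The point should be corrected, but it does not threaten the trial's main conclusion.

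**What to change.** In SAP 6.9.6, replace the sentence on how SD is measured with a rule along these lines:

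*SD counts towards CBR only if an evaluable assessment at the week-16 visit (on or after study day 106, that is, week 16 minus the 7-day window) or later shows no PD, and there is no PD on or before that assessment. Otherwise the patient is counted as not having clinical benefit. The 16-week requirement is met by the week-16 visit, window included.*

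The last sentence is needed because a scan on day 106 computes to 15.14 weeks under SAP 6.1.2. For the same reason, do not add a rule that runs SD duration to the last scan without PD, since it would contradict the visit-window rule for scans on days 106 to 111. A cut-off at day 106 remains, but it sits at the edge of the allowed window, so all on-schedule week-16 scans are treated alike. The rule also settles patients who never meet PD.

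The cost is SAP wording and one derivation from dates already collected. CBR may be slightly lower, and it will differ from a PD-date convention, so show the PD-date version as a labelled sensitivity analysis. Patients with ongoing SD who have no scan from day 106 onward at the data cutoff would count as not benefiting, and their number should be reported. If the relevant database lock has passed, keep the PD-date CBR as the planned result and give the week-16 version as the sensitivity analysis.

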6.9.7. Progression-Free Survival (PFS)

PFS is defined as the number of months elapsed between the date of the first dose and the earliest date of documented disease progression or death (whatever the cause). IRC assessments will serve as the principal data source. Additional analyses based on investigator assessment will be provided. If warranted by data, the analysis methods described for DOR will be used for PFS. Patient-level listing of PFS will be provided.

PFS will be calculated as follows:

$$\text{PFS (months)} = (\text{Event or Censoring Date} - \text{First Dose Date} + 1) / 30.4375$$

PFS will be right-censored for patients who met one or more of the following conditions:

- No post-baseline disease assessments unless death occurred prior to the first planned assessment (in which case death will be considered a PFS event)
- Subsequent anticancer therapy in the absence of documented disease progression

- Died or documented disease progression after missing two or more consecutively scheduled disease assessment visits
- Alive and without documented disease progression on or before the data cutoff date

If a patient meets more than one of these conditions, then the scenario that occurs first will be used for analysis. The event or censoring date will be determined based on the conventions listed in [Table 6.2](#).

Table 6.2. Date of Event or Censoring for PFS

Situation	Date of event or censoring	Outcome
Death before first planned disease assessment	Date of death	Event
Death or disease progression between planned disease assessments	Date of death or first disease assessment showing disease progression, whichever occurs first	Event
No postbaseline disease assessments	Date of first dose	Censored
Subsequent anticancer treatment started before disease progression or death (without disease progression beforehand)	Date of last evaluable disease assessment prior to start of subsequent anticancer treatment	Censored
Death or disease progression after missing two or more consecutively scheduled disease assessments	Date of last evaluable disease assessment visit without documentation of disease progression before the first missed visit	Censored
Alive and without disease progression	Date of last evaluable disease assessment	Censored

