9.4.3 Efficacy Analyses

The efficacy analyses will be conducted on the efficacy population unless otherwise specified.

Tumor response will be assessed using RECIST 1.1 (Table 11-8). The objective response rate (ORR) is defined as the number of patients who achieve a best overall response of complete response (CR) or partial response (PR) that are confirmed divided by the total number of efficacy analysis population. ORR, accompanied by 2-sided 95% exact binomial CIs, will be summarized. The analysis of ORR will be conducted both by the responses determined by IRC and investigator.

Waterfall plots will be used to depict graphically the maximum decrease from baseline in the sum diameters of target lesions.

DOR will be calculated for patients who achieve CR or PR. For such patients, DOR is defined as the number of months from the start date of CR or PR (whichever response status is observed first) and subsequently confirmed, to the first date that PD is objectively documented. If a patient dies, irrespective of cause, without documentation of PD beforehand, then the patient's date of death will be used to denote the response end date.

PFS will be derived for each patient as the number of months from the date of the first dose of study drug to the earlier of documented PD or death due to any cause. Patients who are alive and without documented PD as of a data analysis cutoff date will be right-censored.

OS will be derived for each patient as the number of months from the date of the first dose of study drug to the date of death, irrespective of cause. Patients who are alive or lost to follow-up as of a data analysis cutoff date will be right-censored. The censoring date will be determined from the last date the patient was known to be alive or data analysis cutoff date, whichever occurs first.

The detailed censoring rule for lifetime data such as DOR, PFS and OS will be specified in SAP. DOR, PFS, and OS will be summarized descriptively using the Kaplan-Meier method with 95%

CI. Median follow-up for each endpoint will be estimated according to the Kaplan-Meier estimate of potential follow-up ([Schemper and Smith 1996](#)).

Analyses of other secondary and exploratory endpoints will be provided in the SAP.

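### SAP 6.9.7 censors at first dose a never-scanned patient who dies between the week-8 and week-16 scans, while another row of Table 6.2 makes the same death an event

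*SAP*

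**What the plan says.** SAP 6.9.7 defines PFS from first dose to documented progression or death from any cause. It then lists conditions for right-censoring, any one of which is sufficient. Two matter here:

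- "No post-baseline disease assessments unless death occurred prior to the first planned assessment". The SAP adds that a death that early is a PFS event. Table 6.2 censors the remaining never-scanned patients at the date of first dose.
- "Died or documented disease progression after missing two or more consecutively scheduled disease assessment visits". Table 6.2 censors these at the last evaluable assessment before the first missed visit.

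Table 6.2 also has an event row, "Death or disease progression between planned disease assessments", dated at death or at the scan that shows progression.

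Protocol 9.4.3 measures PFS "to the earlier of documented PD or death due to any cause". It mentions right-censoring only for patients who are alive without progression, and leaves the detailed censoring rules to the SAP. Protocol Table 7-1 makes the week-4 scan optional and requires scans at week 8 and then every 8 weeks to week 48, each within 7 days either way.

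**The concern.** The first bullet spares only deaths before the first planned assessment. A patient who misses the week-8 scan and dies before week 16 has missed one required scan, yet loses all follow-up. On its wording, the event row in Table 6.2 fits the same patient. The table thus supports two opposite codings, and nothing tells a programmer which applies.

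A patient too ill to attend the first scan who then dies is an informative failure. Censoring on day 1 takes that failure out of both the event count and the risk set.

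The case is plausible. Protocol 4.1 admits ECOG 2 and asks for a life expectancy of at least 3 months, a point inside the week 8 to 16 interval. The end-of-treatment scan is waived if one was done within the previous 8 weeks (Table 7-1 footnote), so a recent baseline scan can excuse it. Imaging after stopping for reasons other than progression is optional, while survival follow-up continues (Protocol 7.6). A death can therefore be on record with no post-baseline scan.

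**Working it through.** The documents state no PFS median, rate, event count or power, so there is no plan figure to reproduce.

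**Inputs.** Required scans at week 8 (56 days after day 1, so day 57) and week 16 (day 113), from Protocol Table 7-1. At least 20 patients in each of Cohorts 1 and 2, from SAP 5.2. PFS in months = (event or censoring date - first dose date + 1) / 30.4375, from SAP 6.9.7; the bracket equals the study day.

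**Step 1: worked patients.**

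| Patient | As the bullets read | If one missed visit is tolerated throughout |
|---|---|---|
| No scan, dies day 50 | Event, 50/30.4375 = 1.64 months | Same |
| No scan, dies day 75 | Censored, 1/30.4375 = 0.03 months | Event, 75/30.4375 = 2.46 months |
| No scan, dies day 112 | Censored, 0.03 months | Event, 112/30.4375 = 3.68 months |
| Scanned week 8, misses week 16, dies day 140 | Event, 140/30.4375 = 4.60 months | Same |

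The second and fourth patients each missed one required scan and died before the next, but are treated in opposite ways. A never-scanned patient who dies after missing both week 8 and week 16 is censored under either bullet, so the inconsistency is confined to the one-missed-visit interval.

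**Step 2: effect on Kaplan-Meier.** Let n be the group size, k all events up to time t, and m the never-scanned deaths in the interval, with t after the last of them and no other censoring.

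- Deaths counted as events: S = (n-k)/n.
- Deaths censored at day 1: n-m patients remain, with k-m events, so S = (n-m-(k-m))/(n-m) = (n-k)/(n-m).
- Ratio: n/(n-m), which exceeds 1 whenever m is at least 1.

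**Step 3: numbers.** Both m and the 70% 6-month PFS (deaths counted) are assumptions.

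| n | m=0 | m=1 | m=2 | m=3 |
|---|---|---|---|---|
| 10 | 70.0% | 7/9 = 77.8% (+7.8) | 7/8 = 87.5% (+17.5) | 7/7 = 100% (+30.0) |
| 20 | 70.0% | 14/19 = 73.7% (+3.7) | 14/18 = 77.8% (+7.8) | 14/17 = 82.4% (+12.4) |
| 40 | 70.0% | 28/39 = 71.8% (+1.8) | 28/38 = 73.7% (+3.7) | 28/37 = 75.7% (+5.7) |

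The n=10 row is relevant because SAP 6.9.1 analyses efficacy by tumor type, where groups may fall below 20.

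**Step 4: with administrative censoring.** A simulation used 4000 runs per setting, exponential PFS, uniform administrative censoring at 9 to 30 months, and n=20 or 40. It assumed medians of 8 to 18 months and 2.5% to 15% of patients dying unscanned between weeks 8 and 16. Mean 6-month PFS rose by 1.5 to 12.0 points, upward in every setting. For n=20, a median of 12 months and 5% such deaths, it was 67.0% with the deaths as events and 70.6% with day-1 censoring; the typical estimated median was 10.2 against 11.7 months.

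**Step 5: the undefined boundary.** The SAP does not say whether the first planned assessment is week 8 or the optional week-4 scan. If week 4 counted, never-scanned deaths from week 4 onward would also be censored. Nor does it say how the 7-day window applies: the nominal interval is day 57 to day 113, and with 7 days added at both ends it is day 64 to day 120.

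**The case against.** The strongest reply is that the bullet is explicit. It settles the coding of never-scanned patients, so the clash with the event row is loose table wording. The two-missed-visits bullet is one sufficient reason to censor; it does not say that a death after a single miss must be an event. Both remarks are fair, but an explicit rule can still be out of step with the rest of its section, and nothing says that the bullet overrides the event row.

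A reader might infer three stronger things that the documents do not support:

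- That the tie-break (the scenario occurring first prevails) selects day-1 censoring. It ranks only the censoring conditions against each other, and this patient meets just one. The bullet alone produces the result.
- That the SAP breaches Protocol 9.4.3. The protocol counts death from any cause but delegates detailed censoring to the SAP, so this is a drafting gap in the SAP.
- That early deaths in general are removed. Deaths before the first planned assessment remain events.

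The affected group may also be small or empty. Protocol 4.1 requires a life expectancy of at least 3 months, a week-4 scan is encouraged, an end-of-treatment scan is asked for if none is recent, and unscheduled scans are collected. Any evaluable post-baseline scan takes the patient out of the rule. PFS is a descriptive secondary endpoint with no test, to be analysed with the DOR methods only if the data warrant it. The death would still count in OS and appear in the listing of deaths, the patient would be in the PFS listing, and a never-scanned patient in the primary analysis set stays in the ORR denominator as a non-responder. All of this limits the consequence; it does not remove the inconsistency.

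**Conclusion.** The point stands, within a narrow scope: never-scanned patients who die after the first planned assessment but before missing a second. For them SAP 6.9.7 leads to day-1 censoring, against the event row in Table 6.2, the section's tolerance of one missed visit elsewhere, and its own definition of PFS. After such a death the Kaplan-Meier estimate is too high.

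The size rests on how many such deaths occur, which the documents do not give. On the assumed 70% at 6 months, one or two deaths among 20 patients add 3.7 or 7.8 points; none adds nothing. It would therefore be wrong to say that reported PFS is biased: it is biased only if such deaths occur. This should be corrected because the rule is ambiguous and can err in only one direction, but it does not touch the primary endpoint.

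**What to change.** Reword the first censoring bullet and the Table 6.2 row for patients without any post-baseline scan. A death without a post-baseline assessment is an event at the date of death if fewer than two consecutive scheduled assessments were missed and no subsequent anticancer therapy was started beforehand; otherwise the patient is censored at first dose. The therapy condition keeps the rule consistent with the existing bullet on subsequent treatment. State also that the first planned assessment is the required week-8 scan with its 7-day window, not the optional week-4 scan.

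The cost is a short SAP amendment and no new data. The revision history places SAP version 3 before the second database lock, so a first lock had presumably already taken place, and the study is open-label; the change should therefore be dated, justified and documented. PFS may come out slightly less favourable.
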